For Cycles 1-8, subjects may have study drug administered up to 2 days before or 3 days after the scheduled dosing date. Subjects may be dosed no less than 12 days from the previous dose. For Cycles 9-17, subjects may be dosed within a +/- 3 day window. A maximum delay of 6 weeks (42 days) between doses of nivolumab (or placebo) during Cycles 1-8 or a maximum delay of 10 weeks (70 days) between doses of nivolumab (or placebo) during Cycles 9-17 are allowed.

4.5.1 *Antiemetic Premedications*

Antiemetic premedications should not be routinely administered prior to dosing of drugs. See [Section 4.5.6](#) for premedication recommendations following a nivolumab related infusion reaction.

4.5.2 *Dose Delay Criteria*

Dose delay criteria apply for all drug-related adverse events. Treatment delays up to 6 weeks (42 days) from the last dose of nivolumab (or placebo) during Cycles 1-8 or up to 10 weeks (70 days) from the last dose of nivolumab (or placebo) during Cycles 9-17 are allowed.

Nivolumab (or placebo) administration should be delayed for the following:

- Any Grade \geq 2 non-skin, drug-related adverse event, with the following exceptions:
 - Grade 2 drug-related fatigue does not require a treatment delay
- Grade 2 drug-related creatinine, AST, ALT or Total Bilirubin abnormalities
- Any Grade 3 skin, drug-related adverse event
- Any Grade 3 drug-related laboratory abnormality (excluding AST, ALT or Total Bilirubin), with the following exceptions for lymphopenia, and asymptomatic amylase or lipase:
 - Grade 3 lymphopenia does not require dose delay
 - Any Grade \geq 3 drug-related amylase or lipase abnormalities that is not associated with symptoms or clinical manifestations of pancreatitis do not require a dose delay.
- Any adverse event, laboratory abnormality, or intercurrent illness which, in the judgment of the investigator, warrants delaying the dose of study medication.

Subjects who require delay of nivolumab should be re-evaluated weekly or more frequently if clinically indicated and resume nivolumab dosing when re-treatment criteria are met.

Note: per BMS standards, the term “interruption” is reserved for interruption of the actual IV infusion during administration. The terms omission and interruption should not be used synonymously when completing the CRF forms.

4.5.2.1 *Adverse Event Management Algorithms for Immuno-Oncology Agents*

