Laboratory Tests	X	On site/local complete blood count (CBC) w/differential, Chemistry panel including: LDH, AST, ALT, ALP, T-Bil, blood urea nitrogen (BUN) or serum urea level, creatinine, Na, K, Cl, total protein, glucose, albumin, amylase, lipase within 14 days prior to randomization. Urinalysis as clinically indicated within 14 days prior to randomization. Endocrine panel (TSH, Free T4, Free T3. Total T3/T4 are acceptable if free T3/T4 are not available), Hep B/C (HBV sAG, HCV antibody or HCV RNA), HIV (when required by local regulations), within 28 days prior to randomization.
Pregnancy Test (WOCBP only)	X	Serum or urine to be done at screening visit and repeated within 24 hours of first dose of study therapy
Efficacy assessment		
Baseline Tumor Imaging Assessment	X	See Section 5.4 After complete resection and within 28 days prior to randomization. Disease-free status should be documented.
IWRS		
IWRS entry	X	IWRS entries must be made as follows: For subject number assignment at the time informed consent is obtained Prior to dosing for study drug vial assignment (call should be made within 3 days prior to dosing)

Table 5.1-2: On-Treatment Procedural Outline (CA209577)

Procedure	Cycle 1 Day 1 (C1D1)	Each cycle on Day 1 (up to 2 days prior to dosing, unless indicated otherwise in the Notes)	Notes Each cycle duration is 2 weeks until 8 doses of nivo/placebo are complete. Remaining subsequent cycles are 4 weeks in duration Treatment is until recurrence or discontinuation from study for maximum treatment duration of 1 year
Safety Assessments			
Targeted Physical Examination	X	X	To be performed within 72 hours prior to dosing
Vital Signs	X	X	Including BP, HR, temperature, Obtain vital signs within 72 hours prior to first dose.
Weight and ECOG Performance Status	X	X	Within 72 hours prior to dosing See Appendix 1 for ECOG Performance Status scale
Adverse Events Assessment	Continuously		Assessed using NCI CTCAE v. 4.0.
Review of concomitant medications	X	X	
Laboratory Tests	X	X	Within 72 hours prior to each dose. Include CBC w/differential, LFT's, BUN or serum urea level, creatinine, Na, K, Cl, LDH, Glucose, amylase, lipase, TSH (with reflexive Free T4 and Free T3. Total T3/T4 are acceptable if free T3/T4 are not available.) ^a Note: Laboratory tests do not need to be repeated if performed within 14 days prior to first dose

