7 STATISTICAL ANALYSES

7.1 General Methods

Unless otherwise noted, discrete variables will be tabulated by the frequency and proportion of subjects falling into each category, grouped by treatment. Percentages given in these tables will be rounded to the first decimal and, therefore, may not always sum to 100%. Percentages less than 0.1 will be indicated as ‘< 0.1’. Continuous variables will be summarized by treatment group using the mean, standard deviation, median, minimum, and maximum values.

Time-to-event variables (e.g. time-to resolution) will be analyzed using the Kaplan-Meier technique. When specified, the median will be reported along with 95% CI using Brookmeyer and Crowley method¹² (using log-log transformation for constructing the confidence intervals¹³).

The conventions to be used for imputing missing and partial dates for analyses requiring dates are described in [Section 8](#).

7.1.1 Adverse Events, Serious Adverse Events, Multiple events, Select Adverse Events, Other Events of Special Interest and Immune-Mediated Adverse Events

Drug-related AEs are those events with relationship to study drug “Related”, as recorded on the CRF. If the relationship to study drug is missing, the AE will be considered as drug-related.

Serious adverse events consist of AEs deemed serious by the Investigator and flagged accordingly in the CRF and clinical database.

Adverse events leading to study drug discontinuation are AEs with action taken regarding study drug(s) = “Drug was discontinued”.

Adverse events leading to dose delay are AEs with action taken regarding study drug(s) = “Drug was delayed”.

Adverse events leading to dose reduction are AEs with action taken regarding study drug(s) = “Dose was reduced”.

Adverse events will be coded using the Medical Dictionary for Regulatory Activities (MedDRA), and the most recent version of the dictionary at the time of the database lock will be used. Adverse event results will be graded for severity using the NCI Common Terminology Criteria for Adverse Events (CTCAE) and the version of the criteria specified in the protocol will be used.

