7.4.1 Administration of Study Therapy

For this study, dosing schedule per protocol is as follows:

- 240mg every 2 weeks for 16 weeks (8 doses) [240mg dosing]
 - Note that a subject has to receive all 8 240mg doses before he/she starts on the 480mg doses. (Even if, due to dose delays, a patient would receive his/her 8th 240mg dose later than Week 16.)
- 480mg every 4 weeks beginning at Week 17 (2 weeks after the 8th dose) [480mg dosing]

The following parameters will be summarized (descriptive statistics) by treatment group:

- Number of doses received
- Cumulative dose
- Relative dose intensity (%) using the following categories: $< 50\%$; $50 - < 70\%$; $70 - < 90\%$; $90 - < 110\%$; $\geq 110\%$
- Duration of treatment

Duration of study therapy will be summarized (descriptive statistics) by treatment group.

Duration of study therapy will be calculated using a KM curve whereby the last dose date will be the event date for those subjects who are off study therapy. Subjects who are still on study therapy will be censored on their last dose date. Median duration of treatment and associated 95% CI will be provided.

A by-subject listing of dosing of study medication (record of study medication, infusion details, and dose changes) will be also provided.

Table 7.4-1: Administration of study therapy: definition of parameters

Nivolumab
Dosing schedule per protocol

Table 7.4-1: Administration of study therapy: definition of parameters

Nivolumab	
Dose	
  240mg dosing: ratio of Total Volume Infused with Total Volume Prepared x 240 in mg  480mg dosing: ratio of Total Volume Infused with Total Volume Prepared x 480 in mg 
Volume infused/prepared in mL at each dosing date is collected on the CRF.

Cumulative Dose	The sum of all doses (mg) administered to a subject during the treatment period
Relative dose intensity (%)	$100 \times \frac{\text{cumulative dose (mg)}}{(\text{Last dose date of nivo} - \text{first dose date of nivo} + X) \times \frac{120 \text{ (mg)}}{7 \text{ (days)}}$ 
X is 14 days if the last dose of nivolumab the patient plans to receive is 240mg; X is 28 days if the last dose of nivolumab the patient plans to receive received is 480mg.

Duration of study therapy	Last dose date - Start dose date + 1

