7.4.2 Modifications of Study Therapy

7.4.2.1 Dose Delays

Per protocol, a dose will be considered as actually delayed if the delay is exceeding 3 days. The maximum delay allowed between doses (for both nivolumab and placebo) is 42 days. Dose delay is defined as follows:

- 240mg dosing: duration of preceding cycle in days - 14
- 480mg dosing: duration of preceding cycle in days - 28

Dose delays will be divided into following categories: on-time, 4 - 7 days, 8 - 14 days, 15 - 42 days, 43 - 70 days, > 70 days. Reason for dose delay will be retrieved from CRF dosing pages.

The following parameters will be summarized by treatment arm:

- Number of dose delayed per subject, Length of Delay and Reason for Dose Delay.

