7.4.2.2 Infusion Interruptions and Rate Changes

Per protocol, there will be no dose escalations or reductions of study therapy allowed. Subjects may be dosed no less than 12 days (240mg dosing) or 26 days (480mg dosing) from the previous dose.

Each nivolumab or placebo infusion can be interrupted and/or the IV infusion rate can be reduced. This information will be retrieved from CRF dosing pages.

The following parameters will be summarized by treatment group:

- Number of subjects with at least one dose infusion interruption, the reason for interruption, and the number of infusion interruptions per subject.
- Number of subjects with at least one IV infusion rate reduction, the reason for reduction and the number of infusion with IV rate reduction per subject.

[REDACTED]

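### The dose-delay rule subtracts 28 days at the first 480 mg dose, which is due 14 days after dose 8, so Cycle 9 delays of 4 to 17 days are tabulated as on time

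*SAP*

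**What the plan says.** SAP 7.4.2.1 counts a dose as delayed when the delay is more than 3 days. It groups delays as on time, 4-7, 8-14, 15-42, 43-70 and more than 70 days, and summarises their number, length and reason by arm. The delay is the length of the preceding cycle minus 14 days for 240 mg dosing; for 480 mg dosing it is "480mg dosing: duration of preceding cycle in days - 28".

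The 480 mg label is attached to the schedule in SAP 7.4.1: "480mg every 4 weeks beginning at Week 17 (2 weeks after the 8th dose"). Protocol Table 4.5-1 assigns 240 mg to Cycles 1-8 and 480 mg to Cycles 9-17. Protocol Table 5.1-2 gives the cycle lengths: "Each cycle duration is 2 weeks until 8 doses of nivo/placebo are complete", and four weeks after that.

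The limit on delays in Protocol 4.5.2 runs from the previous dose: "Treatment delays up to 6 weeks (42 days) from the last dose of nivolumab (or placebo) during Cycles 1-8", and 70 days during Cycles 9-17.

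**The concern.** Cycle 9 is the one dose at which the dose level and the length of the interval before it do not match. It is a 480 mg dose, but it follows a 14-day cycle. A programmer who applies the 480 mg line to every 480 mg dose takes 28 days off an interval planned at 14, so each Cycle 9 delay comes out 14 days too short.

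The consequence is that the count and length of delays are understated for subjects who are late at the switch. The exposure outputs would also disagree with each other. Relative dose intensity in Table 7.4-1 handles the switch properly, so it can fall because of a late Cycle 9 dose that the delay table calls on time. AEs leading to dose delay come from the action-taken field on the CRF (SAP 7.1.1), so an AE table could also show a delay that the exposure table does not.

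**Working it through.** **Inputs.** Doses 1-8 are 14 days apart and Cycle 9 comes 14 days after dose 8 (SAP 7.4.1; Protocol Table 5.1-2). Later doses are 28 days apart. The threshold and categories are those of SAP 7.4.2.1.

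**Schedule.** Counting the first dose as day 1, Cycles 1-8 fall on days 1, 15, ..., 99. Cycle 9 falls on day 113 (the start of Week 17, since 112/7 = 16 full weeks have passed). Cycles 10-17 fall on days 141, ..., 337. That is 17 doses and 16 intervals.

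**The rule on an on-schedule subject, with the label taken as the dose being given.**
- Cycles 2-8: 14 - 14 = 0. Correct.
- Cycle 9: 14 - 28 = -14. Still reported as on time, but offset by two weeks.
- Cycles 10-17: 28 - 28 = 0. Correct.

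**A late Cycle 9 dose.** For a true delay of d days, the score is (14 + d) - 28 = d - 14. It exceeds 3 only when d is 18 or more.

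| True delay d (days) | Score d - 14 | Correct category | Category reported |
|---|---|---|---|
| 0-3 | -14 to -11 | on time | on time |
| 4-7 | -10 to -7 | 4-7 | on time |
| 8-14 | -6 to 0 | 8-14 | on time |
| 15-17 | 1 to 3 | 15-42 | on time |
| 18-21 | 4 to 7 | 15-42 | 4-7 |
| 22-28 | 8 to 14 | 15-42 | 8-14 |
| 29-42 | 15 to 28 | 15-42 | 15-42 |
| 43-56 | 29 to 42 | 43-70 | 15-42 |
| 57-70 | 43 to 56 | 43-70 | 43-70 |
| 71-84 | 57 to 70 | > 70 | 43-70 |
| 85 or more | 71 or more | > 70 | > 70 |

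**How much of the permitted range is affected.** The protocol does not make plain which limit governs the gap after dose 8.
- If it is 42 days, the largest permitted delay is 42 - 14 = 28 days. All 25 whole-day values from 4 to 28 are misfiled (14 + 4 + 7).
- If it is 70 days, the largest is 70 - 14 = 56 days. Of the 53 values from 4 to 56, 25 + 14 = 39 are misfiled.

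Protocol 4.5.5 allows longer gaps in some cases, so the lower rows of the table can still occur.

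**Comparison with relative dose intensity.** Table 7.4-1 divides cumulative dose by (last dose date - first dose date + X) x 120/7, with X chosen by the last dose level: "X is 14 days if the last dose of nivolumab the patient plans to receive is 240mg", and 28 days for 480 mg. If dose 9 is the last dose, the cumulative dose is 8 x 240 + 480 = 2400 mg and the intensity is 100 x 2400 / [(112 + d + 28) x 120/7]:
- d = 0: 2400/2400 = 100%.
- d = 14: 2400/2640 = 90.9%, while the delay rule gives 0 days.
- d = 28: 2400/2880 = 83.3%, while the delay rule gives 14 days.

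**The other reading.** If the label describes the preceding cycle, Cycle 9 is scored as (14 + d) - 14 = d, and all 16 intervals are correct.

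**The case against.** The strongest reply is that the label is shorthand for the cycle being measured. The natural figure to subtract from a cycle's actual length is its planned length, and Cycle 8 is a 240 mg cycle of 14 days. The choice of X in the dose-intensity formula follows the same logic, since it ties the interval to the dose that opens it. This is a reasonable guess at the intent, but the SAP does not state it, and its other uses of the label point the other way. SAP 7.4.1 starts 480 mg dosing with the Week 17 dose. The Dose row of Table 7.4-1 uses the label for the dose being infused: "480mg dosing: ratio of Total Volume Infused with Total Volume Prepared x 480 in mg". SAP 7.4.2.2 uses it for the dose about to be given: "Subjects may be dosed no less than 12 days (240mg dosing) or 26 days (480mg dosing) from the previous dose". That last rule is weaker evidence, because taken literally it would bar an on-schedule Cycle 9 dose; the switch may simply have been overlooked there as well.

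The conflict with dose intensity should not be overstated. The example above, with dose 9 as the last dose, shows it at its largest, and 90.9% is still in the SAP's 90 to < 110% band. For a subject who receives all 17 doses (6240 mg) and is late only at Cycle 9, the intensity is 100 x 6240 / [(336 + d + 28) x 120/7], which is 96.3% at d = 14 and 92.9% at d = 28, both in that band.

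It is also fair to say that the counts 25 of 25 and 39 of 53 are of possible day values, not subjects. The documents give no frequency of late Cycle 9 doses, so the number of table entries affected is unknown. The by-subject dosing listing would still show the actual dates.

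**Conclusion.** The concern holds. Followed as written, the rule understates every Cycle 9 delay by 14 days and reports delays of 4 to 17 days as on time. This rests on taking the label as the dose being given, which is how the SAP uses it elsewhere; under the other reading nothing is misfiled. Confidence that the literal reading is the one a programmer would apply is moderate.

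The importance is minor. The rule touches one interval per subject who reaches Cycle 9, applies equally to both arms, and has no shown effect on the comparison between them. Doses given on time are still reported as on time, and the efficacy analyses, the alpha allocation, dose intensity and the CRF-based AE tables do not use it.

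**What to change.** Define the delay by cycle number: days since the previous dose minus 14 for Cycles 2-9, including the first 480 mg dose, and minus 28 for Cycles 10-17. This is correct under either reading. The cost is one line of SAP text and one line of code. The Protocol's rationale for Revised Protocol 04 says the first interim analysis is complete, so exposure tables may already exist; the sponsor should check which reading the program used. If it scored Cycle 9 against 14 days, only the wording changes. If it used 28, the delay table needs to be rerun.

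Two editorial points could be tidied at the same time; neither affects outputs. The single 42-day maximum in SAP 7.4.2.1 should match the protocol's 42 days (Cycles 1-8) and 70 days (Cycles 9-17). The 26-day minimum in SAP 7.4.2.2 should match the protocol's window of plus or minus 3 days and allow for the 14-day interval before Cycle 9.

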7.4.2.2 Infusion Interruptions and Rate Changes

Per protocol, there will be no dose escalations or reductions of study therapy allowed. Subjects may be dosed no less than 12 days (240mg dosing) or 26 days (480mg dosing) from the previous dose.

Each nivolumab or placebo infusion can be interrupted and/or the IV infusion rate can be reduced. This information will be retrieved from CRF dosing pages.

The following parameters will be summarized by treatment group:

- Number of subjects with at least one dose infusion interruption, the reason for interruption, and the number of infusion interruptions per subject.
- Number of subjects with at least one IV infusion rate reduction, the reason for reduction and the number of infusion with IV rate reduction per subject.

[REDACTED]

7.4.3.1 Immune modulating medication

Immune modulating concomitant medications are medications entered on an immune modulating medication form or available from the most current pre-defined list of immune modulating medications. The list of anatomic class, therapeutic class and generic name used for the selection at the time of the database lock will be provided.

The percentage of subjects who received immune modulating concomitant medication for

- management of adverse event
- premedication
- other use
- any use
- management of drug-related select adverse event (any grade, grade 3-5) by select AE category/subcategory (EU/ROW Submissions)
- management of IMAEs (any grade, grade 3-5) by IMAE category (US Submission)

will be reported separately for each treatment group (percentages of treated subjects by medication class and generic term).

For each category/subcategory of drug-related select AEs (any grade, grade 3-5) and IMAEs (any grade, grade 3-5), the following will be reported for each treatment group:

- The total immune modulating medication treatment duration (excluding overlaps), duration of high dose of corticosteroid, initial dose of corticosteroid, and tapering duration (summary statistics)

Duration represents the total duration the subject received the concomitant medication of interest. If the subject took the medication periodically, then DURATION in the summation of all use. Initial dose represents the dose of the concomitant medication of interest received at the start of

the event. In the case multiple medications started on the same date, the highest equivalent dose is chosen and converted to mg/kg by dividing by the subject's recent weight.

These analyses, except the ones related to IMAEs will be conducted using the 30-day safety window. The analyses related to IMAEs will be conducted using the 100-day safety window.

7.4.3.2 Subsequent Cancer Therapy

Number and percentage of subjects receiving subsequent therapies will be summarized. Categories include:

- Immunotherapy including commercial Nivolumab (anti-PD1 agents, anti-PD-L1 agents, anti-CTLA-4 agents and others) by drug name
- Other anti-cancer agents excluding all immunotherapy (approved and investigational) by drug name
- Surgery for treatment of tumors
- Radiotherapy for treatment of tumors
- Any combination of the above

A subject listing of follow-up therapy will also be produced for subjects who had any subsequent therapy.

7.5 Efficacy

7.5.1 Strong Control of Type I Error

For the analysis purposes of the primary endpoint of DFS and the first secondary endpoint of OS, the overall hierarchical approach¹¹ will be used to strongly control family-wise error rate of 0.05 across 2 endpoints and repeated DFS and OS analyses at interim and final analyses.

[figure not shown]
Let $i = 1, 2$ denote index indicating the primary endpoint DFS and the first secondary endpoints OS respectively. Accordingly, H_1 and H_2 denote two-sided null hypotheses of no effect in primary endpoint DFS and the first secondary endpoint OS. Let $t = 1, 2, 3$ denote index indicating the analysis timing. Correspondingly, $p_{i,t}$ denote the nominal p-value of testing H_i at the analysis time t , and the corresponding decision boundaries can be expressed as nominal significance levels $\alpha_{i,t}$ such that H_i is rejected if $p_{i,t}$ is smaller than $\alpha_{i,t}$ at time t .

The nominal significance levels for DFS at the interim and final DFS analyses $\alpha_{1,1}$ and $\alpha_{1,2}$ will be computed using EAST software based on a generalization of the Lan-DeMets error spending function approach using an O'Brien-Fleming stopping boundary given overall two-sided $\alpha = 0.05$. The stopping boundary will depend on the actual number of DFS events observed at the time of the DFS interim and final analysis.

Test of OS will be performed following the overall hierarchical testing procedure¹¹ upon demonstration of superiority in DFS analysis at DFS IA or DFS FA for all randomized subjects. Once OS receives the full alpha from DFS, the Lan-Demets alpha spending function with O'Brien-

Fleming Boundaries will be used to determine the significance level $\alpha_{2,1}$ and $\alpha_{2,2}$ and $\alpha_{2,3}$ for OS at each analysis. The alpha will be adjusted based on actual number of OS events observed.

Figure 4: Testing Strategy for the Primary Endpoint of DFS and the Secondary Endpoint of OS

Specifically, at the interim analysis time of DFS, H_1 is tested with nominal significance level $\alpha_{1,1}$, leading to the following two possibilities of rejecting H_1 :

- If $p_{1,1} < \alpha_{1,1}$, H_1 (DFS) will be rejected, and H_2 (OS) will be tested with nominal significance level $\alpha_{2,1}$, leading to the following two possibilities of rejecting H_2 (OS):
 - If $p_{2,1} < \alpha_{2,1}$, H_2 (OS) will be rejected.
 - If $p_{2,1} \geq \alpha_{2,1}$, H_2 (OS) will not be rejected, and the trial continues to the IA2 OS analysis. At the IA2 OS analysis, H_2 (OS) is tested with nominal significance level $\alpha_{2,2}$, leading to the following two possibilities of rejecting H_2 (OS):
 - If $p_{2,2} < \alpha_{2,2}$, H_2 (OS) will be rejected.
 - If $p_{2,2} \geq \alpha_{2,2}$, H_2 (OS) will not be rejected, and the trial continues to the FA OS analysis. At the FA OS analysis, H_2 (OS) is tested with nominal significance level $\alpha_{2,3}$, leading to the following two possibilities of rejecting H_2 (OS):
 - If $p_{2,3} < \alpha_{2,3}$, H_2 (OS) will be rejected.
 - If $p_{2,3} \geq \alpha_{2,3}$, H_2 (OS) will not be rejected.
- If $p_{1,1} \geq \alpha_{1,1}$, H_2 (OS) will not be tested at the interim analysis of DFS and the trial continues to the FA DFS analysis. At the FA DFS analysis, H_1 (DFS) is tested with nominal significance level $\alpha_{1,2}$, leading to the following two possibilities of rejecting H_1 (DFS):

- If $p_{1,2} < \alpha_{1,2}$, H_1 (DFS) will be rejected, and H_2 (OS) will be tested with nominal significance level $\alpha_{2,2}$, leading to the following two possibilities of rejecting H_2 (OS).
 - If $p_{2,2} < \alpha_{2,2}$, H_2 (OS) will be rejected, and the trial will stop.
 - If $p_{2,2} \geq \alpha_{2,2}$, H_2 (OS) will not be rejected, and the trial continues to the final OS analysis. At the FA OS analysis, H_2 (OS) is tested with nominal significance level $\alpha_{2,3}$, leading to the following two possibilities of rejecting H_2 (OS):
 - If $p_{2,3} < \alpha_{2,3}$, H_2 (OS) will be rejected.
 - If $p_{2,3} \geq \alpha_{2,3}$, H_2 (OS) will not be rejected.
- If $p_{1,2} \geq \alpha_{1,2}$, H_2 (OS) will not be tested, and the trial will be considered as not meeting the primary objective.

If the analysis is performed with the event number exactly the same as those specified in [Table 5.1-3](#), the alpha allocation for DFS and OS is as specified in Table 7.5.1-1. For example if the timing of the interim DFS analysis is performed exactly at 85% of all 440 DFS events (374 DFS events), the boundary in terms of statistical significance for declaring superiority would be $\alpha_{1,1} = 0.03$. The boundary for declaring superiority in terms of statistical significance for the final DFS analysis after 440 DFS events would be 0.042. The significance levels for the final DFS analysis will be adjusted according to the actual alpha spent at the interim analysis and the actual number of DFS events at the interim and final analyses.

The significance levels for the final OS analysis will be adjusted according to the actual alpha spent at interim analysis 1 and interim analysis 2 and the actual number of OS events at OS interim analysis 1, interim analysis 2, and final analysis.

Table 7.5.1-1: Alpha Allocation if the Analysis is Performed with the Event Number Exactly the Same as Specified.

Analysis Timing	DFS		OS	
	Event Number (%of all events)	Alpha	Event Number (%)	Alpha
IA DFS & IA1 OS	374 (85%)	$\alpha_{1,1} = 0.03$	299 (65%)	$\alpha_{2,1} = 0.01$
FA DFS & IA2 OS	440	$\alpha_{1,2} = 0.042$	368 (80%)	$\alpha_{2,2} = 0.022$
FA OS	NA	NA	460	$\alpha_{2,3} = 0.042$

